7.2 Demographic and Other Baseline Characteristics

At Screening, the following demographic data will be collected: date of birth, sex (gender), race, and ethnicity. Information about previous and concomitant medications taken within 4 weeks prior to randomization and the number of documented relapses within 1 year of randomization will be collected.

Medical history data (including diagnosis and duration of MS) will be recorded and a complete physical exam, will be performed. Medical history includes both disease and medication history. Vital signs, including oral temperature, heart rate, respiratory rate, semisupine blood pressure, weight, and height will be obtained. All other Baseline measures, such as safety laboratory parameters, Quantiferon-TB test, ECG, and CXR will be assessed. Baseline disease will be assessed by EDSS and MRI.

7.3 Efficacy Assessments

The following efficacy assessments will be undertaken, as outlined in the Schedule of Assessments (Table 1, Table 2, and Table 3). During treatment, i.e., Day 1 to Week 48 (or up to Week 384 for the OLE Period), all assessments should be completed prior to the administration of study medication.

7.3.1 Brain Magnetic Resonance Imaging Scans

MRI scans will be performed at Screening, at 4-week intervals from Week 12 to 24, and at the End of Treatment Visit at Week 48 (including for participants receiving Tecfidera who choose to enter

the OLE Period). For participants in the OLE Period, an MRI will also be performed at Day 1 (except for participants who received Tecfidera during the 48-week parent study and had an MRI at the End of Treatment Visit at Week 48), Week 48, and then every 48 weeks up to and including the OLE End of Treatment Visit. If a participant discontinues the study more than 4 weeks after his or her most recent MRI, an MRI may be obtained at the 4-week Safety Follow-up Visit. The Screening MRI scan should be acquired before randomization and dosing to allow for the readouts to be read by the central MRI reader (approximately 7 days).

Gadolinium will be used to enhance T1-weighted lesions and to optimize clarity and accuracy of reporting. As gadolinium is excreted renally, participants with acute renal insufficiency (eGFR < 45 mL/min/1.73 m²) will be excluded from the trial (see Section 5.3.2, exclusion criterion 33).

Brain MRI scans will be performed according to a standardized imaging protocol before and after the administration of single-dose gadolinium.

Images will be assessed and reported by an independent, blinded, centralized MRI reading service, provided by PPD.

The assessment will be performed in the absence of clinical information. Further details, including the scans required and the optimal MRI workflow, will be provided in a separate Imaging Manual that will be provided to each trial site by PPD.

All MRI images will be reviewed and reported locally by a radiologist for safety. The local report will contain only nonMS pathology and will be provided to the Treating Investigator.

Note: Where possible, the use of high dose corticosteroids should be avoided in the 3-week period prior to a scheduled MRI scan. In participants receiving corticosteroids for an MS relapse, there must be a 3-week interval between the last dose of corticosteroids and the scheduled MRI scan.

In addition, if a scheduled MRI scan is delayed or an unscheduled MRI scan is indicated, care should be taken to avoid the participant being exposed to gadolinium more than once in a 4-week period, i.e., it may be necessary to cancel the MRI scan at the next scheduled visit (all other assessments should be completed at the visit as normal). If the next scheduled visit is the End of Treatment Visit (Week 48), the Week 48 MRI scan should be performed as soon as the 4-week period since previous exposure to gadolinium has elapsed. See also Section 7.1.3.

7.3.2 Expanded Disability Status Scale

A standard neurological examination will be performed by an Assessing Neurologist and the participant's level of disability will be assessed using the EDSS as outlined in Table 1, Table 2, and Table 3.

The EDSS is an ordinal clinical rating scale ranging from 0 (normal neurological examination) to 10 (death due to MS) in half-point increments and should be administered in person by a neurologist trained in its use (19).

The EDSS score is calculated after neurologic testing and examination of the following eight functional systems, areas of the central nervous system that control bodily functions:

• Pyramidal (ability to walk);

- Cerebellar (coordination);
- Brain stem (speech and swallowing);
- Sensory (touch and pain);
- Bowel and bladder functions;
- Visual;
- Mental;
- Other (includes any other neurological findings due to MS).

Steps will be taken to eliminate inter- and intra-rater variability in the administration and assessment of the EDSS in the trial. The EDSS should be administered by an Assessing Neurologist who has undergone trial-specific EDSS training prior to the start of the trial and the same individual should evaluate a given participant throughout the course of the trial. The EDSS assessment should take place at approximately the same time of day and a standardized protocol should be followed for the neurologic examination.

Further information regarding the EDSS assessment will be provided in the Laboratory Manual.

7.3.3 Relapse Assessment

Participants will be assessed for MS relapse at visits as outlined in Table 1, Table 2, and Table 3, beginning at Week 4. Relapse will also be assessed at any Unscheduled Visit for Neurological Worsening and Relapse Assessment (see Section 7.1.4). For participants in the OLE Period, MS relapse will be assessed at all visits. A qualifying relapse is defined as new, worsening or recurrent neurological symptoms attributed to MS that last for at least 24 hours without fever or infection, or adverse reaction to prescribed medication, preceded by a stable or improving neurological status of at least 30 days. This relapse must be accompanied by new clinical signs (i.e., changes in the neurological examination or an increase in EDSS score).

All cases of potential relapse should be objectively confirmed by the Investigator regardless of whether they are identified during a scheduled or unscheduled visit. Any assessments needed to confirm the relapse should be performed, and details of the relapse should be documented within the relevant section(s) of the eCRF. The criteria for a protocol-defined relapse should be clear and there should be documentation of how each potential relapse did or did not meet the criteria. Participants who have a documented relapse during treatment are not required to discontinue treatment unless they meet any of the criteria for withdrawal from the trial therapy (see Section 5.6.1) or withdrawal from the trial, including the need for treatment with a nonpermitted medication (see Section 5.6.2).

A nonqualifying relapse is any other relapse as defined by the Investigator that does not meet the qualifying relapse definition.

7.4 Assessment of Safety

The safety profile of the IMP will be assessed through the recording, reporting and analysis of baseline medical conditions; AEs; physical examination findings including vital signs, ECGs, and laboratory tests (including Ig and subclass concentration and CCI cell counts).

Comprehensive assessment of any apparent toxicity experienced by each participant will be performed from the time of giving informed consent and throughout the trial. The Investigator will report any AEs, whether observed by the Investigator or reported by the participant (see Section 7.4.1.2). The reporting period for AEs is described in Section 7.4.1.3.

7.4.1 Adverse Events

7.4.1.1 Adverse Event Definitions

Adverse Event

An AE is any untoward medical occurrence in a participant or clinical investigation participant administered a pharmaceutical product, regardless of causal relationship with this treatment. An AE can therefore be any unfavorable and unintended sign (including an abnormal laboratory finding), symptom, or disease temporally associated with the use of a medicinal product, whether or not considered related to the medicinal product.

For surgical or diagnostic procedures, the condition/illness leading to such a procedure is considered as the AE rather than the procedure itself.

The Investigator is required to grade the severity or toxicity of each AE.

Investigators will reference the National Cancer Institute-Common Terminology Criteria for AEs (NCI-CTCAE), Version 4.03 (publication date: 14 June 2010) (20), a descriptive terminology that will be provided in the Manual of Procedures that can be used for AE reporting.

A general grading (severity/intensity; hereafter referred to as severity) scale is provided at the beginning of the above referenced document, and specific event grades are also provided.

Only if a particular AE's severity is not specifically graded by the guidance document, the Investigator is to use the general NCI-CTCAE definitions of Grade 1 through Grade 5 following his or her best medical judgment.

The 5 general grades are:

- Grade 1 or Mild;
- Grade 2 or Moderate;
- Grade 3 or Severe:
- Grade 4 or Life-threatening;

• Grade 5 or Death.

According to Sponsor convention, any clinical AE with severity of Grade 4 or Grade 5 must also be reported as an SAE. However, a laboratory abnormality of Grade 4, such as anemia or neutropenia, is considered serious only if the condition meets 1 of the serious criteria described below.

If death occurs, the primary cause of death or event leading to death should be recorded and reported as an SAE. "Fatal" will be recorded as the outcome of this specific event and death will not be recorded as a separate event. Only, if no cause of death can be reported (e.g., sudden death, unexplained death), the death per se might then be reported as an SAE.

Investigators must also systematically assess the causal relationship of AEs to IMP using the following definitions. Decisive factors for the assessment of causal relationship of an AE to the IMP include, but may not be limited to, temporal relationship between the AE and the IMP, known side effects of IMP, medical history, concomitant medication, course of the underlying disease, trial procedures.

Unrelated: Not reasonably related to the IMP. AE could not medically (pharmacologically/clinically) be attributed to the IMP under study in this clinical trial protocol. A reasonable alternative explanation must be available.

Related: Reasonably related to the IMP. AE could medically (pharmacologically/clinically) be attributed to the IMP under study in this clinical trial protocol.

Abnormal Laboratory Findings and Other Abnormal Investigational Findings

Abnormal laboratory findings and other abnormal investigational findings (e.g., on an ECG trace) should not be reported as AEs unless they are associated with clinical signs and symptoms, lead to treatment discontinuation or are considered otherwise medically important by the Investigator. If a laboratory abnormality fulfills these criteria, the identified medical condition (e.g., anemia, increased ALT) must be reported as the AE rather than the abnormal value itself.

Serious Adverse Events

An SAE is any untoward medical occurrence that at any dose:

- Results in death;
- Is life-threatening. (Note: The term "life-threatening" refers to an event in which the participant is at risk of death at the time of the event, not an event that hypothetically might have caused death if it was more severe):
- Requires inpatient hospitalization or prolongs an existing hospitalization, except in the case of hospitalizations due to protocol-defined relapses;
- Results in persistent or significant disability or incapacity;
- Is a congenital anomaly or birth defect;

• Is otherwise considered to be medically important. (Note: Important medical events that may not result in death, be life-threatening, or require hospitalization may be considered as SAEs when, based upon appropriate medical judgment, they may jeopardize the participant or may require medical or surgical intervention to prevent 1 of the outcomes listed above. Examples of such events include allergic bronchospasm requiring intensive treatment in an emergency room or at home, blood dyscrasias or convulsions that do not result in inpatient hospitalization, or the development of drug dependency or drug abuse.)

For the purposes of reporting, any suspected transmission of an infectious agent via an IMP is also considered an SAE, as described in 7.4.1.4.

Events that Do Not Meet the Definition of an SAE

Elective hospitalizations to administer, or to simplify trial treatment or trial procedures (e.g., an overnight stay to facilitate IV therapy) are not considered SAEs. However, all events leading to unplanned hospitalizations or unplanned prolongation of an elective hospitalization (e.g., undesirable effects of any administered treatment) must be documented and reported as SAEs, except for unplanned hospitalizations due to relapse of MS.

Events Not to Be Considered as AEs/SAEs

Medical conditions present at the initial trial visit that do not worsen in severity or frequency during the trial are defined as Baseline medical conditions and are not to be considered AEs.

Worsening of the underlying disease is not routinely to be considered an AE or SAE, but is rather an efficacy endpoint, unless deemed to be causally related to the IMP.

However, if significant adverse signs or symptoms occur in association with complications or a prolonging of a hospitalization originally due to relapse or disease progression, then these specific complications or hospital prolongation events should be recorded as AEs.

7.4.1.2 Methods of Recording and Assessing Adverse Events

At each trial visit, the participant will be queried on changes in his or her condition. During the reporting period, any unfavorable changes in the participant's condition will be recorded as AEs, whether reported by the participant or observed by the Investigator.

Complete, accurate and consistent data on all AEs experienced for the duration of the reporting period (defined below) will be reported on an ongoing basis in the appropriate section of the eCRF. All SAEs must be additionally documented and reported using the appropriate Report Form as described in Section 7.4.1.4.

It is important that each AE report include a description of the event, its duration (onset and resolution dates and times when it is important to assess the time of AE onset relative to the recorded treatment administration time), its severity, its causal relationship with the trial treatment, any other potential causal factors, any treatment given or other action taken, including dose

modification or discontinuation of the IMP, and its outcome. In addition, serious cases should be identified and the appropriate seriousness criteria documented.

Specific guidance can be found in the eCRF Completion and Monitoring Conventions provided by the Sponsor.

7.4.1.3 Definition of the Adverse Event Reporting Period

The AE reporting period for safety surveillance begins when the participant is initially included in the trial (date of first signature of informed consent/date of first signature of first informed consent) and continues until the 4-week Safety Follow-up/End of Trial Visit for participants who are not transitioning into the long-term follow-up study under a new protocol or until OLE End of Treatment Visit for participants transitioning into the long-term follow-up study under a new protocol.

Any SAE assessed as related to IMP must be reported whenever it occurs, irrespective of the time elapsed since the last administration of IMP.

7.4.1.4 Procedure for Reporting Serious Adverse Events

Serious Adverse Events

In the event of any new SAE occurring during the reporting period, the Investigator must immediately (within a maximum of 24 hours after becoming aware of the event) inform the Sponsor or its designee using the SAE Report Form, which must be completed by the Investigator following specific completion instructions.

For names, addresses, telephone and fax numbers for SAE reporting, see information included in the Adverse Event Safety Report Form.

In exceptional circumstances, an SAE (or follow-up information) may be reported by telephone; in these cases, the eCRF must be completed.

Relevant pages from the eCRF may be provided in parallel (e.g., medical history, concomitant drugs). Additional documents may be provided by the Investigator, if available (e.g., laboratory results, hospital report, autopsy report). In all cases, the information provided on the SAE Report Form must be consistent with the data about the event recorded in the eCRF.

The Investigator must respond to any request for follow-up information (e.g., additional information, outcome, final evaluation, other records where needed) or to any question the Sponsor/designee may have on the AE within the same timelines as those noted above for initial reports. This is necessary to ensure prompt assessment of the event by the Sponsor or designee and (as applicable) to allow the Sponsor to meet strict regulatory timelines associated with expedited safety reporting obligations.

Requests for follow-up will usually be made via the responsible Medical Monitor, although in exceptional circumstances the Global Drug Safety department may contact the Investigator directly to obtain further information or to discuss the event.

7.4.1.5 Safety Reporting to Health Authorities, Independent Ethics Committees/ Institutional Review Boards and Investigators

The Sponsor or designee will send appropriate safety notifications to Health Authorities in accordance with applicable laws and regulations.

The Investigator must comply with any applicable site-specific requirements related to the reporting of SAEs (particularly deaths) involving trial participants to the IEC/IRB that approved the trial.

In accordance with ICH GCP, the Sponsor/designee will inform the Investigator of "findings that could adversely affect the safety of participants, impact the conduct of the trial or alter the IEC's/IRB's approval/favorable opinion to continue the trial." In particular and in line with respective regulations, the Sponsor/designee will inform the Investigator of AEs that are both serious and unexpected and are considered to be related to the administered product ("suspected unexpected serious adverse reactions" or SUSARs). The Investigator should place copies of Safety Reports in the Investigator Site File. National regulations with regard to Safety Report notifications to Investigators will be taken into account.

When specifically required by regulations and guidelines, the Sponsor/designee will provide appropriate Safety Reports directly to the concerned lead IEC/IRB and will maintain records of these notifications. When direct reporting is not clearly defined by national or site-specific regulations, the Investigator will be responsible for promptly notifying the concerned IEC/IRB of any Safety Reports provided by the Sponsor/designee and of filing copies of all related correspondence in the Investigator Site File.

For trials covered by the European Directive 2001/20/EC, the Sponsor's responsibilities regarding the reporting of SAEs/SUSARs/Safety Issues will be carried out in accordance with that Directive and with the related Detailed Guidance documents.

7.4.1.6 Monitoring of Participants with Adverse Events

AEs are recorded and assessed continuously throughout the trial (see Section 7.4.1.3) and are assessed for final outcome at the 4-week Safety Follow-up/End of Trial Visit for participants who are not transitioning into the long-term follow-up study under a new protocol. For participants transitioning into the long-term follow-up study under a new protocol, AEs are assessed for final outcome at the OLE End of Treatment Visit.

All SAEs ongoing at the 4-week Safety Follow-up/End of Trial Visit for participants who are not transitioning into the long-term follow-up study under a new protocol and at the OLE End of Treatment Visit for participants transitioning into the long-term follow-up study under a new protocol must be monitored and followed up by the Investigator until stabilization or until the outcome is known, unless the participant is documented as "lost to follow-up". Reasonable

attempts to obtain this information must be made and documented. It is also the responsibility of the Investigator to ensure that any necessary additional therapeutic measures and follow-up procedures are performed.

7.4.2 Pregnancy and In Utero Drug Exposure

Only pregnancies considered by the Investigator to be related to trial treatment (e.g., resulting from a drug interaction with a contraceptive medication) are considered to be AEs. However, all pregnancies with an estimated conception date during the period defined in Section 7.4.1.3 must be recorded by convention in the AE page/section of the eCRF. The same rule applies to pregnancies in female participants and to pregnancies in female partners of male participants. The Investigator must notify the Sponsor/designee in an expedited manner of any pregnancy using the Pregnancy Report Form, which must be transmitted according to the same timeline as described for SAE reporting in Section 7.4.1.4.

Investigators must actively follow-up, document and report on the outcome of all these pregnancies, even if the participants are withdrawn from the trial.

The Investigator must notify the Sponsor/designee of these outcomes using the Pregnancy Report Form. If an abnormal outcome occurs, the SAE Report Form will be used if the participant sustains an event and the Parent-Child/Fetus Adverse Event Report Form if the child/fetus sustains an event.

Any abnormal outcome must be reported in an expedited manner as described in Section 7.4.1.4, while normal outcomes must be reported within 45 days after delivery.

In the event of a pregnancy in a participant occurring during the course of the trial, the participant must be discontinued from trial medication immediately. The Sponsor/designee must be notified without delay and the participant must be followed as mentioned above.

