M2951 (25 mg tablets) will be administered orally daily for 48 weeks as needed based on the dose (e.g., 3×25 mg tablets for a 75 mg dose). Dosing will be either 25 mg once daily, 75 mg once daily, or 75 mg twice daily. Matched placebo tablets will be provided. For participants who choose to enroll in the OLE, M2951 may be administered for a total of up to 432 weeks.

Reference therapy: dose/mode of administration/dosing schedule: Tecfidera (120 or 240 mg hard capsules) will be used as an active control. For the first 7 days, Tecfidera is administered orally at 120 mg twice daily. Following this and for the duration of treatment, Tecfidera is administered orally at 240 mg twice daily orally. Detailed recommendations for the use of this product are described in the summary of product characteristics or prescribing information.

Planned trial and treatment duration per participant: Total duration of participation is approximately 440 to 448 weeks for participants who choose to participate in the optional OLE Period and approximately 392 days (56 weeks) for participants who do not participate in the optional OLE Period. Total duration includes:

- Screening: 28 days (4 weeks);
- Treatment: 168 days (24 weeks);
- Blinded treatment extension: 168 days (24 weeks);
- Tecfidera Washout for participants who were in Tecfidera arm: 4 to 8 weeks;
- Optional OLE Period (up to 384 weeks);
- 4-week Safety Follow-Up/End of Trial Visit: 28 days (4 weeks).

After completing the 48-week main study, participants will be offered the opportunity to participate in an optional OLE Period with M2951 up to 384 weeks.

Once the long-term follow-up study is open for enrollment in their country (i.e., once the Sponsor, upon agreement with Health Authorities/Ethics Committees, will have notified sites), participants in the OLE Period will have the option to transition into the long-term follow-up study under a new protocol for continued treatment. Upon Sponsor site notification, all participants will be asked to return for an OLE End of Treatment Visit within 30 days.

- For participants entering the long-term follow-up study under a new protocol, their OLE End of Treatment Visit in the current study is also their first visit in the long-term follow-up study. Therefore, these participants are neither required to enter the 4-week Safety Follow-up Period nor to undergo a 4-week Safety Follow-up Visit/End of Trial Visit.

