5.3.1 Inclusion Criteria

- 1. Participants with a diagnosis of RMS (may include participants with SPMS with superimposed relapses provided they meet the other criteria) in accordance with revised McDonald criteria for MS (14, 15) and Lublin and Reingold (16).
- 2. Male or female aged 18 to 65 years.
- 3. One or more documented relapses within the 2 years before Screening with either:
 a) One relapse which occurred within the last year prior to randomization
 or
 - b) the presence of at least 1 Gd+ T1 lesion within 6 months prior to randomization would make the patient eligible.
- 4. EDSS score of 0 to 6 at Baseline.
- 5. Women of childbearing potential must use a supplementary barrier method together with a highly effective method of contraception (according to ICH guidance M3[R2]) for 4 weeks prior to randomization, throughout the trial, and for 90 days after the last dose of IMP. For the purposes of this trial:
 - Women are considered of childbearing potential unless they are postmenopausal. Females who are postmenopausal (age-related amenorrhea ≥ 12 consecutive months and increased FSH > 40 mIU/mL) or who have undergone hysterectomy or bilateral oophorectomy are exempt from pregnancy testing. If necessary to confirm postmenopausal status, an FSH will be drawn at Screening.
 - Highly effective contraception includes:
 - Combined (estrogen and progestogen containing) hormonal contraception associated with inhibition of ovulation; oral, intravaginal or transdermal;
 - Progestogen-only hormonal contraception associated with inhibition of ovulation; oral, injectable or implantable;
 - Intrauterine device (IUD);
 - Intrauterine hormone-releasing system (IUS);
 - Bilateral tubal occlusion;
 - Vasectomized partner;
 - Sexual abstinence.
 - Supplementary barrier methods include:
 - Male or female condom with or without spermicide;
 - Cap, diaphragm or sponge with spermicide.
 - Men must agree to use and have their female partners use a supplementary barrier method together with a highly effective contraceptive method as defined above for at least 90 days after the last IMP administration.

- Women of childbearing potential must have a negative serum pregnancy test at the Screening Visit and a negative urine pregnancy test at randomization on Day 1 before dosing.

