- Details of any overdose with the study drug that may have occurred since the last on-site visit/phone call.

In addition, if a participant is due to be contacted to confirm and discuss at-home pregnancy testing, this can be covered in the same phone call (women of childbearing potential only).

7.1.7 **Open-label Extension End of Treatment Visit**

Once the long-term follow-up study is open for enrollment in their country (i.e., once the Sponsor, upon agreement with Health Authorities/Ethics Committees, will have notified sites), participants in the OLE Period will have the option to transition into the long-term follow-up study under a new protocol for continued treatment. Upon Sponsor site notification, all participants will be asked to return for an OLE End of Treatment visit within 30 days.

- For participants entering the long-term follow-up study under a new protocol, their OLE End of Treatment Visit in the current study is also their first visit in the long-term follow-up study. Therefore, these participants are neither required to enter the 4-week Safety Follow-up Period nor to undergo a 4-week Safety Follow-up Visit/End of Trial Visit.
- Participants who do not wish to transition into the long-term follow-up study, will have the OLE End of Treatment Visit followed by a 4-week Safety Follow-up Visit/End of Trial Visit.

In case the long-term follow-up study will not become available in their respective country, participants will complete the OLE per study schedule and have the OLE End of Treatment Visit at Week 384 followed by a 4-week Safety Follow-up Visit/End of Trial Visit.

Thus, the OLE End of Treatment Visit will be performed at Week 384 (\pm 14 days) or earlier, if the long-term follow-up study is open for enrollment. Participants will undergo assessments as described in Table 3.

4-week Safety Follow-up/End of Trial Visit 7.1.8

The Safety Follow-up/End of Trial Visit will be performed at Week 52 \pm 5 days for participants who do not participate in the OLE Period or 28 days (± 7-day window) after the OLE End of Treatment Visit for participants who participate in the OLE Period. There will be only one 4-week Safety Follow-up/End of Trial Visit per participant, and the assessments performed will be the

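### For participants who do not transition, pregnancy recording stops about 28 days after the last dose while contraception is required for 90, leaving about 62 post-dose days without a clear recording rule

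*Protocol*

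**What the plan says.** Three parts of the protocol bear on this.

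- **Contraception (Section 5.3.1, criterion 5).** Women of childbearing potential must use contraception "for 4 weeks prior to randomization, throughout the trial, and for 90 days after the last dose of IMP". Men and their female partners must do so "for at least 90 days after the last IMP administration".
- **Pregnancy recording (Section 7.4.2).** The rule is that "all pregnancies with an estimated conception date during the period defined in Section 7.4.1.3 must be recorded", on the adverse event page of the eCRF. It covers female participants and female partners of male participants. Investigators must follow these pregnancies to outcome, even after withdrawal.
- **The period referred to (Section 7.4.1.3).** It starts at consent and "continues until the 4-week Safety Follow-up/End of Trial Visit for participants who are not transitioning". For the others it runs "until OLE End of Treatment Visit for participants transitioning into the long-term follow-up study under a new protocol".

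Section 7.1.8 places the safety visit at Week 52 ± 5 days in the main study, or "28 days (± 7-day window) after the OLE End of Treatment Visit" in the open-label extension (OLE). Section 5.6.2 places it 4 weeks after the last dose for participants who withdraw while on drug. Tables 1 and 3 show the last scheduled pregnancy test at that visit. Section 3.2 lists embryo-fetal toxicity as an important potential risk and gives it as the reason for contraception during the study and for some time afterwards.

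**The concern.** The protocol names a potential harm to the fetus, sets a 90-day post-dose precaution against it, and then borrows the general adverse event window to decide which pregnancies are recorded. That window closes after less than a third of the 90 days. A conception on, say, day 50 after the last dose falls inside the precaution but outside the period on which eCRF recording depends. Outcome follow-up is worded as applying to the pregnancies so defined.

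What is at stake is the completeness of the pregnancy data. Reports that arrive only when something goes wrong give no count of normal outcomes to set beside the abnormal ones. Section 7.4.2 asks for both kinds. No contact is scheduled after the 4-week visit, so a later pregnancy comes to light only if the participant volunteers it and the site decides that it must be recorded.

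**Working it through.** The documents give no figure of their own here, so there is nothing to reproduce. The check compares the stated windows.

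**Inputs**
- Post-dose contraception period: 90 days (Section 5.3.1).
- End of the recording period, non-transitioning participants: the 4-week visit, nominally day 28 after the last dose (Sections 7.4.1.3, 5.6.2, 7.1.8). This takes the last dose to fall at about the End of Treatment Visit.
- Visit windows: ±7 days in the OLE (day 21 to 35) and ±5 days in the main study (day 23 to 33).
- Treatment length: 48 weeks = 336 days in the main study; up to 432 weeks = 3,024 days with the OLE (Synopsis).

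**Step 1: share of the post-dose period outside recording**

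Uncovered days = 90 − visit day; share = uncovered days / 90.

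| Visit day | Uncovered days | Share of 90 |
|---|---|---|
| 28 (nominal) | 62 | 68.9% |
| 35 (OLE, latest) | 55 | 61.1% |
| 21 (OLE, earliest) | 69 | 76.7% |
| 33 (main, latest) | 57 | 63.3% |
| 23 (main, earliest) | 67 | 74.4% |

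**Step 2: share of the whole period under the contraception rule once treatment starts**

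Treatment time lies wholly inside the recording period. Share = 62 / (treatment days + 90).

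- 48 weeks: 62 / (336 + 90) = 62 / 426 = 14.6%.
- 432 weeks: 62 / (3,024 + 90) = 62 / 3,114 = 2.0%.
- The share passes one half only if 62 / (T + 90) > 0.5, that is, if treatment lasted T < 34 days.

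Reading these as shares of conceptions would need a constant conception rate over the whole period. The documents do not supply that, so they are shares of time.

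**Step 3: does any other text close the gap?**

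- Section 7.4.2 also requires expedited notification of pregnancies on the Pregnancy Report Form, in a sentence with no time limit of its own. It follows directly after the conception-date rule, so a site could read it as limited by that rule or as free-standing.
- Section 7.4.1.3 makes any related SAE reportable whenever it occurs, and Section 7.4.1.1 counts a congenital anomaly or birth defect as serious. This reaches only serious outcomes judged related to study drug.
- No text sets a recording period reaching day 90.

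**Exceptions to day 28**
- Section 7.1.2 tells early discontinuers in the main study to return for the 4-week visit immediately, whereas Section 5.6.1 puts that visit 4 weeks after an End of Treatment Visit. On the first reading the gap widens.
- Tecfidera participants found ineligible for the OLE after washout have a later End of Trial Visit (Section 5.5.1), so their gap is smaller.

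**The case against.** A reader might infer that most conceptions at risk would go unreported. The documents do not support that, for two reasons. The contraception requirement covers the whole of treatment as well as the 90 days, and every on-treatment conception is inside the recording period. Step 2 puts the uncovered part at 2% to 15% of that time for participants who complete treatment. And the reporting routes in Step 3 stay open after the 4-week visit, so days 29 to 90 are unclear, not shut out. Both points stand and set the size of this one.

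It can also be said that the 90 days are a precaution, not a derived risk window. Criterion 5 is framed around study drug, which by the definition opening protocol Section 6 includes placebo and Tecfidera. Section 3.2 says that nonclinical data suggest no male-mediated developmental risk, and it refers to a short half-life. That is fair: the documents do not show that conceptions on days 29 to 90 carry drug risk, or that they are needed to assess it. The point is narrower. The protocol asks participants to avoid conception for a stated period and does not clearly ask sites to record conceptions in most of it.

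Finally, no planned analysis depends on this. SAP Section 17.7 only lists pregnancy tests, and SAP Section 17.2.3 does not name embryo-fetal toxicity among the events of special interest. That limits the weight of the point but does not remove the mismatch.

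**Conclusion.** The mismatch is in the text. For participants not moving to the long-term study, about 62 of the 90 post-dose days (69%; 55 to 69 days, 61% to 77%, with the OLE visit window) have no clear eCRF recording or outcome follow-up rule. It is a limited gap in safety data collection, with no bearing on efficacy, power or alpha.

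This rests on the 4-week visit falling about 28 days after the last dose, and on using the contraception period as the yardstick for recording. It does not extend to transitioning participants: their recording here ends at the OLE End of Treatment Visit, but they continue treatment under a protocol that is not among these documents.

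The change is worth making because it is cheap and concerns a risk that the protocol itself lists as important.

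**What to change.** Reconcile Sections 5.3.1, 7.4.1.3 and 7.4.2. Give pregnancies their own recording period in Section 7.4.2, separate from the general adverse event window and matched to whatever post-dose period the protocol requires for contraception. State that the notification sentence and outcome follow-up apply over that same period. Collection can rely on participants telling the site and the investigator notifying the sponsor, or on one phone call. No new visit or test is needed.

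Add a line that this does not extend the end-of-trial definition in Section 5.8. Without it, a protocol-defined follow-up period could keep the trial open.

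The cost is a protocol clarification, a consent-sheet update (with additional consent where Section 10.5 calls for it), and occasional notifications or one call per participant. No dose or contraception rule needs to change.
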